3.3.3 Twenty-four Hour Follow-up

Twenty-four hours post V1 (and subsequent imaging visits) the subjects will be contacted by phone and questioned regarding any post MRI adverse events. (Refer to Table 2 for the scheduled of events.)

Table 2: Scheduled of Events

Protocol Activities	Screening (V0)	Study Visit (V1)	Follow Up (24 hours by phone)
Informed Consent	X		
General Medical History	X		
Physical Exam	X		
HRCT ¹	X		
Weight and Height	X		
Concomitant Medication	X		
Pregnancy Test (serum and urine) ²	X		
Quality of Life Assessment	X		
MRI Screening Form	X	X	
Vital Signs Assessment	X	X	
Pulse oximetry	X	X	
Six Minute Walk Test	X		
Thermally Polarized Gas MRI			X
Pulmonary Function Test	X		
Adverse Event Assessment		X	X
¹ depending on scheduling, the HRCT will be performed at screening (V0) or between screening (V0) – study visit (V1)			
² Females of child-bearing potential who had a blood pregnancy tests performed, will have a urine pregnancy test if blood test was given 48 or more hours earlier			

3.4 Product Accountability

In accordance with ICH, we will have proper documentation with regards to product accountability. The documentation will include the following information: the gas type, dates (e.g. order, receive, certification and expiration), ALHCH Lot (or Cylinder #), and ALHACH park #.

The Cylinder # (ALHCH lot) and gas type will be included on each subject's CRF for product accountability purpose.

3.5 Data Identification

According to ICH and FDA guidance, the following data will be considered source and will be recorded directly into each subject's CRFs.

- Screening (V0)
 - Informed Consent date
 - General Medical History
 - Physical Exam
 - Weight/Height
 - Concomitant Medications
 - Quality of Life Assessment
 - Vital Signs
 - Pulse Oximetry
 - 6 Minutes Walk
 - PFT First section
- Study Visit (V1)
 - Vital Signs (pre and post imaging)
 - Pulse Oximetry (pre and post imaging)
 - For Women of child bearing potential
 - Date of the results of the pregnancy test
 - Adverse Events (post imaging)
- 24hr Follow up phone call
 - Adverse Event
 - Follow-up

The following data will be considered source but will not be recorded directly into each subject's CRFs. This data will likely be found in the subject's research folder (paper) and/or electric medical record.

- Informed Consent
- For Women of child bearing potential
 - Result of pregnancy test
- MRI screening Form
- HRCT reading
- PFT Testing results

The CRFs, the MR/HRCT images and PFT testing results will serve as source documents for this study.

4 Selection of Subjects and Withdrawal/Discontinuation

4.1 Inclusion/Exclusion Criteria for Subjects with COPD

Inclusion criteria

Subjects must meet all of the following inclusion criteria to be eligible for enrollment into the

trial

1. Outpatients of either gender, age > 18.
2. Willing and able to give informed consent and adhere to visit/protocol schedules.
(Consent must be given before any study procedures are performed.)
3. Women of childbearing potential must have a negative serum pregnancy test. This will be confirmed before participation in this investigational protocol.
4. Clinical diagnosis of COPD confirmed by Spirometry demonstrating FEV1/FVC <0.70.

Exclusion criteria

Subjects presenting with any of the following will not be included in the trial:

1. Abuse of alcohol or illicit substances.
2. Medical conditions, which, in the opinion of the investigator, will significantly affect five-year survival.
3. Medical or psychological conditions which, in the opinion of the investigator, might create undue risk to the subject or interfere with the subject's ability to comply with the protocol requirements.
4. Conditions that will prohibit MRI scanning (metal in eye, claustrophobia, inability to lie supine, renal insufficiency with eGFR < 60 mL/min/1.73 m²)

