3.3 Duration

3.3.1 Screening (V0)

1. Obtaining Informed Consent from each subject
2. History and Physical exam. The history will focus on onset of symptoms, co-morbidities, and smoking/occupational/environmental history. Also included:
 - a. An assessment of patterns of exacerbations (mild = use of oral antibiotics and/or steroids for an acute change in respiratory status; moderate = hospital admission for a change in respiratory status; severe = requirement for mechanical ventilation for a change in respiratory status).
 - b. A measurement of the body mass index (BMI).
 - c. A medication history (oral steroids, chronic bronchodilator use, oxygen use) with an emphasis on whether adherence was adequate.
 - d. Assessment of gastro-esophageal reflux disease (10)
 - e. Epworth Sleepiness Scale as a marker of sleep disordered breathing

- f. Estimate of daily physical activity (25)
- 3. Pulmonary function tests will include spirometry, plethysmographic lung volumes, and corrected carbon monoxide diffusing capacity (DLCO). All procedures will be done in accordance with ATS/ERS standards (3) (15) (17).
- 4. High resolution computerized scans of the chest (HRCT). Emphysema scores will be calculated per COPD Gene protocol (7). We will also explore novel approaches to quantifying airway structures (5) (16)
- 5. A six-minute walk test with monitoring of pulse oximetry and heart rate will be conducted in accordance with ATS standards (1)
- 6. Vital Signs will be measured and recorded (temperature, heart rate, blood pressure and respiratory rate)
- 7. Pulse oximetry will be measured and recorded.
- 8. Weight and height will be recorded.
- 9. Quality of Life (QOL) will be assessed using the St George self-administered instrument
- 10. A serum pregnancy test will also be performed in women with child bearing potential.

MRI will be collected at the study visit 1 after the screening visit. Where possible the screening visit (V0) and MRI visit (V1) will be accomplished on the same day for the convenience of the subject. In all cases, the MRI will be followed-up immediately following the MRI procedure for any adverse events. Finally, all subjects will be contacted 24 hours post-MRI by phone for follow-up regarding any adverse events.

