4.5 Concomitant Medication

There will be no restriction on participation based on medication use. The following concomitant medication will be recorded.

- **Beta Adrenergic agents**
- **Non-selective agents**
 - Alprenolol
 - Carteolol
 - Levobunolol
 - Mepindolol
 - Metipranolol
 - Nadolol
 - Oxprenolol
 - Penbutolol
 - Pindolol
 - Propranolol
 - Sotalol
 - Timolol
- **β1-Selective agents**
 - Acebutolol
 - Betaxolol
 - Atenolol
 - Bisoprolol

- Metoprolol
- Nebivolol
- Amosulalol
- Landiolol
- Tilisolol
- **Mixed α 1/ β -adrenergic antagonists**
 - Arotinolol
 - Carvedilol
 - Celiprolol
 - Labetalol
- **Quaternary ammonium compound**
 - Ipratropium
 - Tiotropium
- **Inhaled Bronchodilators**
 - Albuterol
 - Arformoterol
 - Metaproterenol
 - Salmeterol
 - Terbutaline
 - Formoterol
 - Levabuterol
 - Pirbuterol
 - Fenoterol
- **Inhaled corticosteroids**
 - Beclomethasone
 - Budesonide
 - Ciclesonide
 - Flunisolide
 - Fluticasone Propionate
 - Monetasone Furoate
 - Triamcinolon
- **Leukotriene blockers**
 - Montelukast
 - Zafirlukast
 - Zileutol
- **Inhaled Combos**
 - Albuterol and pratropium Inhalation
 - Fluticasone Propionate and Salmeterol
 - Budesonide and Formoterol
 - Formoterol and Mometasone
- **Mast Cell Blocker**
 - Chromolyn
- **Bronchodilator**
 - Oxtiphylline
 - Theophylline
- **Oral Steroids**
 - Prednisone
 - Prednisolone
 - Methyl-prednisolone

- **Phosphodiesterase type 4 (PDE-4)**
 - Roflumilast
- **Medical Gas**
 - Oxygen

5 Assessment of Efficacy

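### The protocol requires no clinical stability, so a subject with a current or recent outpatient exacerbation can be staged and scanned in a transient state that affects GOLD stage and gas trapping together

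*Combined protocol and SAP*

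**What the plan says.** All references are to the combined protocol and SAP.

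- **Section 4.1 (COPD subjects).** Besides consent and a negative pregnancy test, entry needs "Outpatients of either gender, age > 18" and "Clinical diagnosis of COPD confirmed by Spirometry demonstrating FEV1/FVC <0.70". The exclusions cover substance abuse, conditions affecting five-year survival, conditions that in the investigator's opinion "might create undue risk to the subject or interfere with the subject's ability to comply with the protocol requirements", and contraindications to MRI. None concerns a current or recent exacerbation.
- **Section 4.2 (normal subjects).** Normal spirometry is required. Recent respiratory infection is not mentioned.
- **Section 4.5.** "There will be no restriction on participation based on medication use". Oral steroids are on the list of medications to be recorded; antibiotics are not.
- **Section 3.3.1.** The V0 history includes "An assessment of patterns of exacerbations (mild = use of oral antibiotics and/or steroids for an acute change in respiratory status"; the moderate grade is hospital admission and the severe grade mechanical ventilation. On timing: "Where possible the screening visit (V0) and MRI visit (V1) will be accomplished on the same day for the convenience of the subject". No maximum interval is set.
- **Table 2 (section 3.3.3).** Pulmonary function is tested at V0. HRCT is done at V0 or between the visits, as scheduling allows.
- **Sections 2 and 3.1.** The design is cross-sectional, and GOLD status is named as an example of the severity measure against which the imaging markers of all aims are evaluated.
- **Section 10.2.** At most one rescan is allowed, in the context of unacceptable image quality.
- **Section 6.1.** No covariate or sensitivity analysis for exacerbation status is named.

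**The concern.** Each COPD subject contributes one staging and one scan, with no planned repeat. The protocol itself defines an exacerbation as an acute change in respiratory status, and nothing in the entry rules keeps that change out of either measurement. When V0 and V1 fall on the same day, as intended where possible, one episode can affect the grouping variable and the outcome at once. The two errors are then correlated, so part of the observed relation between stage and trapping would reflect the same subjects being acutely worse on both measures. When the visits are apart, stage and scan may describe different clinical states, and MR and HRCT trapping in sub-aim 1.1 may do so too.

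The results are meant to identify candidate markers for later longitudinal testing, so a distorted association would be carried into the choice of markers. The sponsor does not treat exacerbations as remote: section 5.2 anticipates significant morbidity and lists exacerbations among the outcome measures. It also says they will not be reported as adverse events, so adverse event records are not a dependable way to find an episode between visits.

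**Working it through.** **1. Does any rule close the gap?**

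| Provision | What it stops | What it leaves open |
|---|---|---|
| Outpatients only (4.1) | Subjects in hospital at enrolment | Episodes treated without admission; recent discharge |
| Investigator exclusion (4.1) | Undue risk, inability to comply | Discretionary; not about validity of the measurement |
| Unable to lie supine (4.1) | The most breathless | Milder episodes |
| SpO2 below 90% (3.3.2) | Hypoxic subjects | Everyone else |
| Exacerbation history (3.3.1) | Nothing; it is collected only | No rule uses it |
| V1 checks (3.3.2) | MRI safety, pregnancy, vital signs, oximetry | Respiratory stability is not asked about |

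The filters block part of the problem. None is a stability rule.

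**2. What does correlated error do?** Treat severity as a continuous score. Let measured severity be S = S0 + E and measured trapping T = T0 + cE, where E is the transient part, taken as independent of the stable values S0 and T0. If b is the stable slope of trapping on severity, the fitted slope tends to

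[b·Var(S0) + c·Var(E)] / [Var(S0) + Var(E)].

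This is a weighted average of the stable slope and the acute within-subject slope c. It does not depend on sample size. It lies above b if c > b and below it if c < b. If the visits are apart and E is present at only one of them, the c term drops out and the slope is diluted. The documents give neither c nor Var(E), so neither direction nor size is determined.

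**3. The plan's own power figures.** Section 6.1 states 90% power at alpha 0.05 for about 6% at 26 per group and 5% at 40 per group, but gives no SD. Using a two-sided noncentral t with noncentrality d/(SD·√(2/n)):

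- 6 points at 26 per group: implied SD 6.54, noncentrality 6/(6.54 × 0.2774) = 3.31.
- 5 points at 40 per group: implied SD 6.81. With SD 6.54 the detectable difference at 40 per group is 4.80, so the two figures agree after rounding.

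**4. Illustration under assumed inputs.** None of these is in the documents: 0.5 to 2 exacerbations a year, 4 to 6 weeks' recovery, visit dates unrelated to episodes, and defect volume D = 5 to 10 points higher during an episode.

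- Share inside the window: p = 1 − exp(−rate × weeks/52). Low: 1 − exp(−0.5 × 4/52) = 3.8%. High: 1 − exp(−2 × 6/52) = 20.6%.
- Mean shift: p × D. Low: 0.0377 × 5 = 0.19. High: 0.2061 × 10 = 2.06 points.
- SD: √(6.5² + p(1 − p)D²). Low: √(42.25 + 0.91) = 6.57. High: √(42.25 + 16.36) = 7.66.

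Probability of a significant result at 26 per group, stable difference 6 points, base SD 6.5 (90.4% with no transient state):

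| p, D | SD | Spread raised in both groups | Spread raised in one group | One group, with its mean shift widening the difference |
|---|---|---|---|---|
| 3.8%, 5 | 6.57 | 89.8% | 90.1% | 92% |
| 20.6%, 5 | 6.81 | 87.6% | 89.0% | 96% |
| 20.6%, 10 | 7.66 | 79.1% | 84.8% | 98% |

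**5. The same illustration as bias.** Take two groups of 26 with equal stable means and base SD 6.6. If 5% of one group is affected with a 3-point rise (shift 0.15), a nominal 5% test rejects 5.1% of the time. If 20% is affected with a 10-point rise (shift 2.0), it rejects 16.6% of the time.

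**The case against.** The strongest reply is that acutely ill subjects are largely filtered out already. They must be outpatients, lie supine and still for about an hour, perform full lung function tests and a six-minute walk, and stay at or above 90% saturation, and the investigator may turn them away. For normal subjects, an infection that impairs spirometry fails entry. This stands in part. It makes the 4% to 21% share in the illustration a poor estimate of true exposure, and it confines the gap mainly to milder episodes and recent recovery. It does not supply a stability rule.

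Some stronger readings are tempting and are not supported:

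- **Power falls from 90% to about 80%.** This needs the top of every assumed range and extra spread in both groups. With one group affected the same corner gives about 85%, and at the mild end power stays near 90%. If the transient rise widens a COPD-versus-normal difference, the chance of significance goes up.
- **An antibiotic-treated episode leaves no trace.** It is missing from the 4.5 list, but the V0 history in 3.3.1 grades a mild episode by "mild = use of oral antibiotics and/or steroids for an acute change in respiratory status", so it should be captured there. A history of patterns does not guarantee a date.
- **Section 4.5 expressly admits subjects on an acute steroid course.** It concerns medication in general, names no acute course, and does not override the investigator exclusion. Broad medication access is reasonable; the absent criterion in 4.1 is the main gap.
- **The effect is largest in GOLD III/IV.** The documents give no stage-specific rate or shift.
- **The protocol aims at stable disease phenotypes.** It does not say so. It seeks candidate markers in a cross-sectional evaluation.

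It is also fair that a transient state shared by same-day MR and HRCT does not in itself invalidate their comparison in sub-aim 1.1.

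**Conclusion.** The point holds as a design weakness. Following the protocol as written, an outpatient with a current or recent exacerbation can be staged and scanned, and the result enters the analysis as that subject's GOLD stage and trapping. The absence of a stability criterion, a deferral rule and an analysis rule is established from the text. That an episode changes airflow and trapping in the same direction is an assumption, as are all the rates and shifts used above.

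The consequence that matters is bias in the stage-trapping association. Its size cannot be computed from the documents; the 0.2 to 2 point shift in a group mean is illustrative, and the filters already in place make the upper end less likely. A reader might infer a general loss of power, but the calculations do not support one. The change is worth making because it is cheap and because, without dated exacerbation information, affected scans cannot be reliably identified afterwards.

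**What to change.** 1. Section 4.1: require no exacerbation, as already defined in 3.3.1, within a fixed window before V0. The investigators set its length.
2. Section 4.2: require no acute respiratory infection within the same window.
3. Section 3.3.1 and the CRF: record the date of the last exacerbation and how it was treated, including antibiotic-treated episodes.
4. Section 3.3.2: repeat the question at V1. Defer and rebook a subject who is inside the window rather than exclude them.
5. Section 6.1: for subjects already scanned inside the window, add a sensitivity analysis of the stage and trapping results without them.

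The cost is a short amendment, one or two CRF items, and some visits delayed by a few weeks. Sample size and treatment are unchanged.

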4.2 Inclusion/Exclusion Criteria for Normal Subjects

Inclusion criteria

Subjects must meet all of the following inclusion criteria to be eligible for enrollment into the trial

1. Outpatients of either gender, age > 18.
2. Willing and able to give informed consent and adhere to visit/protocol schedules.
(Consent must be given before any study procedures are performed.)
3. Women of childbearing potential must have a negative serum pregnancy test. This will be confirmed before participation in this investigational protocol.
4. Normal PFT determined by spirometry.
5. Non-smoker, ex-smoker, or current smoker.

Exclusion criteria

1. Abuse of alcohol or illicit substances.
2. Conditions that will prohibit MRI scanning (metal in eye, claustrophobia, inability to lie supine).

4.3 Subject Withdrawal and/or discontinuation

The reason for a subject discontinuing from the trial will be recorded in the CRF. A discontinuation occurs when an enrolled subject ceases participation in the study, regardless of the circumstances, prior to completion of the protocol. The investigator must determine the primary reason for discontinuation.

When a discontinuation is due to a serious adverse event, the serious adverse event must be reported in accordance with the reporting requirements defined below.

4.4 Treatment of Subjects

4.4.1 MRI

At the study visit (V1), MRI ‘studies’ will be performed using the same MR scanner (a 3.0-Tesla (T) TRIO MRI system (Siemens Medical Systems)). Lung morphology and function will be acquired using conventional ¹H MRI followed by ¹⁹F MRI with a gaseous contrast agent mixed with oxygen for the ¹⁹F MRI study. For both series the subject will lie down in a supine position on the magnet bed inside a transmitter and receive (T/R) coil for imaging of the human torso.

For the gas mixture, the inert medical grade perfluorinated gas (PFP) will be present at 79% combined with 21% medical grade oxygen. The agents will be supplied in aluminum cylinders (MR compatible) at pressures to prevent phase change of the perfluorinated component to the liquid phase. For example, in an 8 inch by 52-inch aluminum cylinder, the same format cylinder of the 79% PFP/21% oxygen mixture will contain 137 liters of the mixture.

Subjects will rest in a supine position for breathing in normal air, and then switch to PFP by a passive Douglas bag system with 35 mm tubing with remote pneumatic switching between room air and PFP and MRI compatible pneumotachometers to allow flow rate and gas volume determinations. The subjects are monitored with an MRI compatible pulse oximeter as well as exhaled % oxygen and carbon dioxide. The subjects will then exit the MRI suite.

4.4.2 High Resolution Computerized Tomography

Chest CT Scan will be performed to assess for emphysema and airway disease in all subjects. An inspiratory chest CT scan will be performed with a radiation dose of 200 mAs in order to provide thorough assessment of small airway wall thickness and emphysema. An expiratory chest CT scan will be performed of lower dose (50 mA) to assess for air trapping.

4.5 Concomitant Medication

There will be no restriction on participation based on medication use. The following concomitant medication will be recorded.

- **Beta Adrenergic agents**
- **Non-selective agents**
 - Alprenolol
 - Carteolol
 - Levobunolol
 - Mepindolol
 - Metipranolol
 - Nadolol
 - Oxprenolol
 - Penbutolol
 - Pindolol
 - Propranolol
 - Sotalol
 - Timolol
- **β1-Selective agents**
 - Acebutolol
 - Betaxolol
 - Atenolol
 - Bisoprolol

- Metoprolol
- Nebivolol
- Amosulalol
- Landiolol
- Tilisolol
- **Mixed α 1/ β -adrenergic antagonists**
 - Arotinolol
 - Carvedilol
 - Celiprolol
 - Labetalol
- **Quaternary ammonium compound**
 - Ipratropium
 - Tiotropium
- **Inhaled Bronchodilators**
 - Albuterol
 - Arformoterol
 - Metaproterenol
 - Salmeterol
 - Terbutaline
 - Formoterol
 - Levabuterol
 - Pirbuterol
 - Fenoterol
- **Inhaled corticosteroids**
 - Beclomethasone
 - Budesonide
 - Ciclesonide
 - Flunisolide
 - Fluticasone Propionate
 - Monetasone Furoate
 - Triamcinolon
- **Leukotriene blockers**
 - Montelukast
 - Zafirlukast
 - Zileutol
- **Inhaled Combos**
 - Albuterol and pratropium Inhalation
 - Fluticasone Propionate and Salmeterol
 - Budesonide and Formoterol
 - Formoterol and Mometasone
- **Mast Cell Blocker**
 - Chromolyn
- **Bronchodilator**
 - Oxtiphylline
 - Theophylline
- **Oral Steroids**
 - Prednisone
 - Prednisolone
 - Methyl-prednisolone

- **Phosphodiesterase type 4 (PDE-4)**
 - Roflumilast
- **Medical Gas**
 - Oxygen

5 Assessment of Efficacy

5.1 Efficacy Parameters

All of the protocols in this proposal will be approved by our Institutional Review Board and reviewed periodically (every 6-12 months). In addition, a local Data Safety and Monitoring Committee (DSMC) will be established. The committee members will be pulmonologists and radiologists with knowledge of COPD, imaging techniques and clinical research procedures. The frequency of monitoring depends on the progress of the study and will range between 3 and 12 months. Any adverse event will be reported to the IRB and DSMC, and serious adverse events will be reported within 24 hours. An annual progress report (or more frequently, if requested) will be submitted to the IRB and DSMC.

5.2 Adverse Event Reporting

Any adverse event will be reported to the IRB and DSMC, and any other regulatory agents, and serious adverse events will be reported within 24 hours. An annual progress report (or more frequently, if requested) will be submitted to the IRB, DSMC and any other regulatory agents.

Significant morbidity and mortality are anticipated in these study subjects due to the nature of the disease. Deaths, exacerbations of COPD, and hospitalizations for any cause are outcome measures of the trial and will not be reported as adverse events. These outcomes will be monitored by the DSMC. In accordance with policies of the NIH, other serious events, including severe injuries and new diagnosis of potentially fatal or disabling medical conditions will be reported as serious adverse events of the study to the local IRB, the DSMC, and the NIH. The clinical investigator(s) will terminate the study immediately if the occurrence of serious adverse events that suggests unacceptable risk to the health of the subjects. All observed or volunteered adverse events, regardless of suspected causal relationship to the study procedure(s), will be recorded on the adverse events page(s) of the CRF's or worksheets. Events involving adverse experiences occurring during the study procedure(s) will be recorded.

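### Section 5.2 exempts deaths, COPD exacerbations and all-cause hospitalisations from adverse event reporting as trial outcomes, but the trial does not follow them as outcomes and its own AE and SAE rules conflict with the exemption

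*Combined protocol and SAP*

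**What the plan says.** Section 5.2 opens with the same general rule as section 5.1, which reads: "Any adverse event will be reported to the IRB and DSMC, and serious adverse events will be reported within 24 hours". It then gives a rationale, "Significant morbidity and mortality are anticipated in these study subjects due to the nature of the disease", and an exemption: "Deaths, exacerbations of COPD, and hospitalizations for any cause are outcome measures of the trial and will not be reported as adverse events". Oversight of the exempt events is covered by one sentence: "These outcomes will be monitored by the DSMC".

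The next sentence sends only the remaining serious events to the local IRB, the DSMC and the NIH: "other serious events, including severe injuries and new diagnosis of potentially fatal or disabling medical conditions will be reported as serious adverse events". The section also says that the investigators "will terminate the study immediately if the occurrence of serious adverse events that suggests unacceptable risk" to subjects' health. It requires every observed or volunteered adverse event to be entered on the CRF whatever its suspected cause, and adds: "Events involving adverse experiences occurring during the study procedure(s) will be recorded".

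**The concern.** Trials sometimes keep endpoint events out of expedited reporting because the endpoint data capture and the monitoring committee already follow them. That justification needs the events to be endpoints. Here they are not, so the exemption removes them from one route without placing them on another.

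At stake is the handling of a death or hospital admission after an investigational gas has been inhaled. Staff following 5.3.2 would report it as serious within 24 hours. Staff following 5.2 would not report it as an adverse event at all. It is also unclear whether such an event would count toward the termination provision in 5.2, which turns on serious adverse events. Because the exemption covers admissions for any cause, it includes one caused by the procedure. Section 1.3.1 itself names asphyxiation, if the gas is breathed without oxygen, as the primary risk of the gas, and describes premixing with oxygen and oximetry as the mitigation.

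**Working it through.** This is a check of text against text. The plan gives no figure to reproduce, and the only arithmetic is counting.

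**1. Are the three event types outcomes of this trial?**

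- *Objectives (section 2):* the evaluation is cross-sectional, and prognostic testing is left to later longitudinal studies.
- *Aims (3.1):* gas trapping during washout, comparison with HRCT, description of the cohort by severity and risk factors, and ventilation defect severity. None is a clinical event.
- *Screening (3.3.1):* exacerbation patterns, including past respiratory admissions and ventilation, are taken as history before the gas is given.
- *Schedule (Table 2) and CRF list (3.5):* after the scan, event capture consists of adverse events at V1 and at the 24-hour call. Section 3.5 also lists a follow-up entry at that call without stating its content. No field is named for death, admission or exacerbation.
- *Follow-up question (5.4):* one open question on health problems since the MRI.
- *Analysis (6.1):* group comparison of ventilation parameters, and models relating MRI features to existing GOLD phenotype and clinical features. The screening history could enter as a predictor or as a clinical feature, but no event after gas exposure is analysed.
- *Longitudinal-sounding text:* 3.3.3 mentions later imaging visits, 4.1 excludes conditions affecting five-year survival, and 6.1 speaks of prognostic indicators. No outcome follow-up is attached to any of these; 10.2 allows a single rescan.

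So none of the three is collected or analysed prospectively as an outcome.

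**2. Does the exemption conflict with the safety rules?**

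| Place | Rule | Against the exemption |
|---|---|---|
| 5.1 and opening of 5.2 | Any AE reported; SAEs within 24 hours | No exception stated in 5.1 |
| 5.3.1 | Worsening of a preexisting illness is an AE | Would include a COPD exacerbation |
| 5.3.2 | Death and inpatient hospitalisation are SAEs | Both are exempted in 5.2 |
| 4.3 | An SAE causing discontinuation follows the reporting rules given later | Inherits whichever reading of 5.2 is used |

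**3. Counts.**

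- Criteria bulleted in 5.3.2: death, life-threatening, hospitalisation, disability, congenital anomaly = 5. Named in the exemption: death and hospitalisation = 2 of 5. The other 3 and the important-medical-event rule are untouched.
- Planned subjects (1.5): 130 COPD + 120 normal = 250; 120/250 = 48% normal.
- Scheduled contact after each scan: one adverse event check immediately afterwards (3.3.1) and one call at 24 hours (3.3.3, 5.4). If the later imaging visits in 3.3.3 mean the one rescan in 10.2, there are at most 2 imaging visits and so at most 2 calls per subject.

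**4. Does DSMC monitoring replace the 24-hour route?** Section 5.2 names no form, route or timing for these events. Section 5.1 sets the frequency of monitoring at between 3 and 12 months, against 24 hours for SAEs. For the exempt events the DSMC is the only recipient named.

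**The case against.** The best defence is that 5.2 is a deliberate exception. A general rule is followed by a specific carve-out, and the word *other* before the remaining serious events shows that it was intended. On this reading 5.3.2 says what an SAE is and 5.2 says what is reported, and 4.3 merely points to whatever 5.2 requires. The point about 4.3 stands: it inherits the conflict and is not an independent contradiction. The rest does not rescue the text. A deliberate exception would still rest on outcomes the trial does not follow, would still cover admissions caused by the procedure, and is not acknowledged in 5.1 or 5.3.1.

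Second, the termination sentence turns on the occurrence of SAEs rather than on their being reported, so a death could still be weighed by the investigators. That is a fair reading. The claim is therefore only that it is unclear whether such a death counts.

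Third, other safeguards remain. Life-threatening events and important medical events are outside the exemption. Suspected procedure-related events are a listed AE type, and adverse experiences during procedures go on the CRF. New potentially fatal or disabling diagnoses are reported. Discontinuation reasons are recorded, regulators, the IRB or the institution can end the trial (6.2), and 9.2 commits the trial to GCP and applicable law. These may well capture the underlying condition, such as a hypoxic event in the scanner. None settles whether the death or admission itself is reported within 24 hours.

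Fourth, the rationale could be read as confining the paragraph to subjects with COPD. That is possible, but the exemption of deaths and hospitalisations carries no cohort limit.

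Finally, a narrower exemption with cross-references could remove the inconsistency between sections. It would still need a reason for exempting the events, and the only one given, that they are outcomes, fails. Section 5.2 also cites NIH policies, for the reporting of the remaining serious events; those policies are not in the documents and no view is taken on them.

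**Conclusion.** The concern holds. Section 5.2 takes three event types out of adverse event reporting on a premise the rest of the protocol does not support, and it conflicts with the protocol's own reporting rules and definitions. As written, 2 of the 5 listed SAE criteria fall within the exemption, and no stated limit keeps it from the 48% of planned subjects who are normal. It needs correction because it governs deaths and admissions after an investigational gas.

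The size in events cannot be estimated: the documents give no event rates, and 5.3.1 refers to an adverse event reporting period whose length is not stated. Scheduled observation is short, so the number captured within it may be small. Events within 24 hours may still be recorded through the phone question, so the defect bears mainly on reporting. The imaging aims and the statistical analysis are not affected. The conclusion assumes that no separate document sets up outcome follow-up for these events; the protocol refers to none.

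**What to change.** Delete from 5.2 the exemption and the statement that these events are outcome measures, and reword the following sentence so that it no longer refers only to the remaining serious events. Reconcile 5.2 with 5.1, 5.3.1 and 5.3.2, so that deaths, hospitalisations and exacerbations in both cohorts are recorded, reported and counted under the protocol's existing AE and SAE definitions, within its adverse event reporting period. Keep DSMC monitoring in addition. The length of that period could usefully be stated in the same amendment; none is proposed here, and the conclusion does not depend on it.

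The cost is protocol wording plus additional safety reports. Their number cannot be forecast from the documents, and 5.2 itself anticipates significant morbidity and mortality. Nothing changes in the imaging procedures, sample size or analysis, and no clinical rule is altered.
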